6.6.2.3 Categorical endpoints

In the analyses of the binary endpoints, multiple imputation will be used to handle missing data at week 24. For week 52 and later, data will not be imputed and only observed values will be used.

The following process describes the multiple imputation for spirometry data (FVC % pred. and SpO₂) and for PedsQL™ point data. Therefore, the words “data” and “value” stand for the data and value of the respective kind of data to be imputed.

In a first step non-monotone missing data will be imputed $m = 100$ times using MCMC (Markov Chain Monte Carlo) to generate m data sets of longitudinal data with monotone missingness pattern. Such a missingness pattern is the pre-requisite for subsequently applying sequential imputation and means that once a patient has a missing value at a particular time point, the corresponding values at all subsequent time points also have missing values. The seemingly large number of imputations ($m=100$) is chosen to minimize the standard error of those estimates that are produced to fill the missing values. The seed number will be set to

1199337. For this step all available data of the respective kind will be used, restricted to one value per patient and analysis time window according to selection process described in [Section 6.7](#) below.

In a second step a regression model including baseline value and measurements at all post-baseline analysis visits scheduled (see [Table 6.7: 1](#) and [Table 6.7: 6](#), respectively) by treatment, will be used to complete the imputation in each dataset.

For each imputed complete dataset, the proportion of non-responders (and the corresponding standard error) will be used for the analysis. The results will be pooled following the standard multiple imputation procedure ([9](#)).

Patients with missing baseline value will be excluded from the analysis.

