While there is overlap between clinical diagnoses associated with lung fibrosis in paediatrics and adults, some diagnoses associated with lung fibrosis are specific to each population. The following paediatric conditions can be most frequently associated with lung fibrosis in paediatrics:

- surfactant protein deficiency (SFTPC and ABCA3 mutations [i.e. recessive disorder, suspected pathogenic variants or deletion/disruption]);
- chronic hypersensitivity pneumonitis (cHP);
- toxic/radiation and drug induced pneumonitis;
- post haematopoietic stem cell transplant (HSCT) fibrosis;
- connective tissue disease related disorders (e.g. juvenile rheumatoid arthritis [RA]/juvenile idiopathic arthritis, SSc, dermatomyositis/polymyositis [DM/PM]; mixed connective tissue disease [MCTD])
- sarcoidosis.

In addition to difference in clinical diagnoses associated with fibrosing lung disease, the clinical course of fibrotic lung disease also differs between paediatrics and adults.

The data on the natural history of chronic fibrosing interstitial lung disease in children is limited. The available evidence suggests overall that the clinical course is associated with better outcome compared to adult ILDs with survival at 2, 4 and 5 years after symptom onset reported to be 83%, 72% and 64%, respectively [[R09-5337](#)]. This is compared to a median survival of 2.5–3.5 years from diagnosis in IPF [[P11-07084](#)], the most progressive form of fibrosing lung disease in adults. However, as previously mentioned there is a subgroup of children with fibrosing lung disease who experience significant morbidity and mortality [[R09-5337](#)].

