7. PLANNED ANALYSIS

Unless otherwise specified, all analyses described in this section will be done on the Treated Set. The labelling and display format of statistical parameters will follow BI standards ([10](#)). For End-Of-Text (EoT) tables, the set of summary statistics is: N / Mean / SD / Min / Median / Max.

In descriptive statistics tables, mean, SD and median will be rounded to one additional digit than the raw individual value. In case some endpoints show some extreme data outside the expected range, quartiles and percentiles will be presented additionally.

Tabulations of frequencies for categorical data will include all possible categories and will display the number of observations in a category as well as the percentage (%) relative to the respective treatment group (unless otherwise specified, all patient in the respective subject set whether they have non-missing values or not). The precision for percentages should be one decimal point. The category missing will be displayed only if there are actually missing values.

Unless otherwise specified, all analyses will be provided by randomized treatment group (placebo or nintedanib) and overall (total).

[figure not shown]
For efficacy and safety end point analyses by time point, as well as for the safety analyses of Part A, patients switching during Part A to Part B will be censored at the time point of the switch and for the safety analyses of Part A (due to the definition of the double-blind period). Patients who started directly in Part B will be analyzed as a separate cohort, in addition to those randomized to nintedanib and those randomized to placebo.

[figure not shown]
All analyses performed after DBL1 will be repeated after DBL2 to include newly emerging data.

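### SAP 6.6.2.3 makes no exception for death: in the FVC, SpO2 and PedsQL responder analyses a child who died before week 24 is imputed, and the week-52 denominator is unclear

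*SAP*

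**What the plan says.** SAP 6.6.2.3 sets two rules. For week 24: "In the analyses of the binary endpoints, multiple imputation will be used to handle missing data at week 24". After that: "For week 52 and later, data will not be imputed and only observed values will be used". Protocol 7.3 gives the same pair of rules.

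The imputation is then set out for particular data: "The following process describes the multiple imputation for spirometry data", which the SAP defines as FVC % predicted and SpO2, and also for PedsQL scores. Gaps in the visit sequence are filled 100 times by MCMC. The remaining values then come from "a regression model including baseline value and measurements at all post-baseline analysis visits scheduled", fitted by treatment. In each completed dataset "the proportion of non-responders (and the corresponding standard error) will be used for the analysis", and the results are pooled. One exclusion is stated: "Patients with missing baseline value will be excluded from the analysis". Neither the SAP section nor Protocol 7.3 mentions death.

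SAP section 7 sets the default denominator for percentages as "all patient in the respective subject set whether they have non-missing values or not", unless something else is specified.

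Death is handled explicitly elsewhere. It is an event in time to first acute ILD exacerbation or death (SAP 5.2.2.12) and in time to death (SAP 5.2.2.13). It is also tabulated among adverse events leading to death and by adjudicated cause (SAP 7.8.1 and 7.8.1.1).

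**The concern.** A value that does not exist because the child has died is not an ordinary missing value. Followed to the letter, the week-24 rule gives that child a lung-function, saturation or quality-of-life value after death and lets the draw decide whether the child responded. Death, the worst outcome of the disease, can then count in part as response.

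The week-52 rule raises a different problem. It does not say whether a child without an observed value leaves the denominator. If so, the response rate describes survivors only.

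Protocol 1.3 says that the efficacy data are meant to support inference about clinical benefit and benefit-risk. Under Protocol 3.1 the benefit-risk assessment at the first database lock decides whether the extension trial starts. SAP section 7 repeats all analyses after the second lock, so an unclear rule would be applied twice. With groups of about 20 and 10, one child is visible in a percentage.

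**Working it through.** The plan gives no figure for these responder analyses, so there is nothing to reproduce first. The check has three parts.

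**1. What the text does with a death**

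- Week 24: the value is missing, baseline is present, and no other exclusion applies, so the value is imputed. The model holds the child's own baseline and scheduled visits, by treatment, but not vital status. For FVC and SpO2 the earlier visits are weeks 2, 6 and 12 (SAP Table 6.7: 1). For PedsQL only the baseline precedes week 24 (Table 6.7: 6).
- Week 52: no observed value exists. If the observed-values rule overrides the section 7 default, the child leaves numerator and denominator. If the default holds, the child stays in the denominator and is not a responder. The SAP does not choose.

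**2. How many deaths might be involved**

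Input: Protocol 1.3.1 reports "survival at 2, 4 and 5 years after symptom onset reported to be 83%, 72% and 64%, respectively". Assumptions: constant hazard, and survival from symptom onset carries over to time from randomisation.

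Hazard h = −ln(S)/years; probability of death by week w is q = 1 − exp(−h × 7w/365.25).

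For S = 0.83 at 2 years, h = 0.0932 per year. By week 24, q = 1 − exp(−0.0932 × 0.460) = 4.2%. By week 52, q = 1 − exp(−0.0932 × 0.997) = 8.9%.

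| Survival used | q, week 24 | Deaths in 30 | q, week 52 | Deaths in 30 |
|---|---|---|---|---|
| 83% at 2 years | 4.2% | 1.3 | 8.9% | 2.7 |
| 72% at 4 years | 3.7% | 1.1 | 7.9% | 2.4 |
| 64% at 5 years | 4.0% | 1.2 | 8.5% | 2.6 |

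The chance of at least one death in 30, 1 − (1 − q)^30, is 68% to 72% by week 24 and 91% to 94% by week 52. Expected deaths by week 24 are 0.7 to 0.8 among 20 nintedanib children and about 0.4 among 10 placebo children.

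**3. What one death does to the rate**

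Inputs: about 20 nintedanib and 10 placebo children (Protocol synopsis); response among survivors r = 50%, assumed. Responders are averages, so fractions occur.

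| Handling of one death | n = 20 | n = 10 |
|---|---|---|
| Non-responder, in denominator | 0.5 × 19/20 = 47.5% | 0.5 × 9/10 = 45% |
| Imputed like a typical survivor | (9.5 + 0.5)/20 = 50% | (4.5 + 0.5)/10 = 50% |
| Observed only, out of denominator | 9.5/19 = 50% | 4.5/9 = 50% |
| Imputed as responder every time | 10.5/20 = 52.5% | 5.5/10 = 55% |

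Handling one death as a typical survivor adds r/n: 2.5 or 5 points at r = 50%. For r from 30% to 70% the range is 1.5 to 3.5 points (n = 20) or 3 to 7 points (n = 10). The ceiling is 1/n, that is 5 or 10 points.

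**The case against.** The strongest reply is that the responder definitions are not in the public text. The visible SAP goes from 5.2.2.13 to 5.4.1.1, and part of the missing-data chapter, between 6.6.2.5 and 6.6.3.3, is also not shown. This SAP tends to put its rules for death in the endpoint definitions, as in the censoring tables of section 5.2.2. A definition that classes death as non-response may exist, and such a child would then not be missing. This stands. A reader might infer that the plan has no rule for death in these analyses anywhere; the documents do not support that. But SAP section 5 refers the handling of missing data points to section 6.6, and 6.6.2.3 instructs imputation without exception. If a definition says otherwise, the two need aligning.

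A reader might also infer that a child who died before week 52 certainly drops out of the denominator. That is not established, because the section 7 default points the other way.

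Nor do deaths vanish from the trial: they remain in two time-to-event endpoints and in the adverse-event tables. The problem does not reach every binary endpoint either. The growth-plate and dental findings are cumulative counts with no response category, and the secondary FVC, SpO2 and PedsQL endpoints are continuous and analysed by MMRM. There is no confirmatory testing.

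The imputation is not blind to decline: for FVC and SpO2 a deteriorating child is imputed partly from that child's own course. This can make a responder draw less likely, but does not exclude it.

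On size, a placebo shift of 10 to 30 points might be inferred from the per-child ceiling. It needs one to three deaths among 10 children, each imputed as a responder every time. At q = 4.2% the chance of three or more placebo deaths by week 24 is 1 − (0.651 + 0.286 + 0.056) = 0.7%. At week 52 there is no longer a concurrent placebo group, because children who complete Part A switch to nintedanib.

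Finally, counting death as non-response is one estimand choice among several. That is true, but the present text makes a choice too, without saying so.

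**Conclusion.** The point holds for the responder analyses of FVC % predicted, SpO2 and PedsQL. At week 24 the stated rule imputes a child who has died and can count that child as a responder in some imputations. From week 52 the denominator is not settled between SAP 6.6.2.3 and section 7.

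The effect is modest but visible: about 2.5 points per death in the nintedanib group and 5 in the placebo group, with ceilings of 5 and 10. This rests on a 50% response among survivors and on groups of 20 and 10. The expected number of deaths rests on a cited cohort followed from symptom onset and on a constant hazard; it sizes the issue and is not a forecast for this trial. The analyses are descriptive and the responder definitions may already address death, so this is a correction that should be made to the missing-data rule and not a threat to the primary results.

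**What to change.** Add to SAP 6.6.2.3 that, in the responder analyses of FVC % predicted, SpO2 and PedsQL, a child who died before the time point is a non-responder, is not imputed, and stays in the denominator at week 24, week 52 and later. Restrict multiple imputation to children not known to have died. Check the sentence against the responder definitions and reconcile it with Protocol 7.3, which carries the same week-24 and week-52 rules.

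The cost is one sentence, one programming condition and the alignment with the protocol. No new data are needed: date of death is already collected for the time-to-death endpoint. If the definitions already class death as non-response, the sentence does no harm and removes the contradiction.

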6.6.2.4 Endpoints based on MRI/x-ray

Patients will complete the baseline MRI/x-ray within the first 2 weeks after randomization. As for the imaging variables we do not expect a change through treatment within the first two weeks wherefore a measurement within the first two weeks can still be considered as baseline in this special case. The same holds for dental examination.

6.6.2.5 6-min walk test (6MWT)

In case the earliest assessment of the 6MWT is on treatment start day after treatment start time, then the whole 6MWT (pre-, during and after) assessment can still be counted as baseline assessment.

[figure not shown]
6.6.3.3 Exposure

6.6.3.3.1 Permanent trial drug discontinuation

A missing or incomplete date of last trial drug intake will be imputed that the derived date is the latest possible date which is on or before date of death, and on or before last contact date from End of Study eCRF page.

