- (**) Patients who discontinue trial treatment prematurely should undergo the End of Treatment (EoT) visit as soon as possible, and follow the trial schedule thereafter, if possible. The patient will be asked to attend all visits (except for the laboratory a-visits) as originally planned until the end of the trial. Please also see Flow Chart footnote 18 for instructions, should the patient be unable to complete the scheduled visits; see [Section 6.2.3](#) for details on trial procedures at these visits. The first visit after the EoT visit will be skipped if the EoT visit occurs within 4 weeks prior to scheduled visit. Patients who did not discontinue trial treatment prematurely should undergo the EoT visit as soon as the timing of final DBL (DBL 2) and EoT visit has been communicated (see [Section 3.1](#) for details). If a regular study visit is scheduled in the period when the EoT visit should be conducted, all procedures required at this regular study visit and the additional procedures, if any, required at the EoT visit will be conducted during the same visit.
- (***) After the EoT visit, patients who completed the treatment period according to protocol will enter a 4-week follow-up period, unless they roll-over into an open label extension trial. See [Section 3.1](#) for details.
- (****) Weeks and Days from the Day of Randomisation, i.e. Day of first intake of randomised medication (D 1).

¹Informed consent (and assent where applicable) will be obtained before any procedure related to the study. When it is obtained before Visit 1, e.g. to allow shipment of images for central review, all Adverse Events (AEs) and Concomitant Treatments occurring after the informed consent have to be recorded, including those occurred between informed consent and Visit 1. The interval between Visit 1 and Visit 2 should be ≤ 28 days. The interval between Visit 1 and Visit 2 could be >28 days in case the assessments required to check inclusion and exclusion criteria cannot be completed within 28 days (e.g. in case the available HRCT scan fails to meet the required image acquisition specification, laboratory test results show out-of-range values requiring retest, etc.) but the screening period (informed consent to Visit 2) must not be longer than 12 weeks. Upon obtaining informed consent, the patient and parent(s)/legal guardian will be instructed on procedures to be followed until the next study visit.

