After the EoT visit, patients will enter a 4-week follow-up period (see [Flow Chart](#) and footnotes for permitted time window), unless they subsequently roll-over into the open label extension trial. The open label extension trial (1199-0378) will be initiated if supported by the benefit-risk assessment from DBL 1.

In the rare case that additional PK data is deemed necessary to complete the primary PK assessment, data from DBL 1 will be updated and the administrative DBL 2 will be postponed. Additional PK will be collected by switching ongoing study participants in Part A to Part B and/or recruiting new patients directly to Part B following screening if supported by the benefit-risk assessment. This decision will be made after discussion with the Safety Monitoring Committee (SMC) and properly documented. Once the decision is taken, all patients who did not yet complete Visit 6 (and were not prematurely discontinued) will be scheduled for Visit 6, complete all visit procedures (see [Section 6.2.2](#) for details) and enter Part B. After two weeks of open label treatment each patient will attend Visit 7, and blood samples for PK analyses will be collected per standard procedures (see [Flow Chart for PK blood sampling](#) for details). If the number of patients in Part A is not sufficient, further patients will be screened and entered to Part B at the end of the screening period, if meeting eligibility criteria (see [Section 3.3.2](#) and [Section 3.3.3](#) for details).

Patients who prematurely discontinued trial medication will be asked to remain in the study and return to all regularly scheduled visits until the end of the trial. For details about procedures to be conducted at these visits please refer to [Section 6.2.3](#). For those patients who are unable to complete the scheduled visits, every attempt will be made to get information on vital status at 24 weeks after randomization (i.e. the time of the data cut-off for the primary analysis), at 52 weeks and at the end of the trial. These requests will be outlined in the parental-information form and discussed during administration of the informed consent (the same applies to the assent form, where applicable).

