- The patient can no longer receive trial treatment for medical reasons (such as adverse events, other diseases, or pregnancy).

If a patient becomes pregnant during the trial the investigational product must be discontinued immediately, and the patient will be followed up until birth or otherwise termination of the pregnancy. The data of the patient will be collected and reported in the clinical trial report (CTR) until patient's last visit, and any events thereafter will be reported in the Boehringer Ingelheim (BI) drug safety database. Refer to [Section 5.2.7.2.3](#) for detailed information on event reporting in case of pregnancy.

In case of discontinuation of trial medication, it is of utmost importance for the robustness and integrity of the trial results that the patient remains in the study and returns to all

regularly scheduled visits until the end of the trial. For those patients who are unable to complete the scheduled visits, every attempt will be made to get information on vital status at 24 weeks after randomization, i.e. the time of the data cut-off for the primary analysis, at 52 weeks after randomization and at the end of the trial, as outlined in the [Flow Chart](#) and [Section 6.2.3](#).

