5.4.3 Exposure

The date of first administration is recorded at visit 2 (day 1) for the blinded period and at visit 6 (week 24) for the open-label period of the trial. The blinded exposure period ends with the first documented intake of the open-label treatment (day of visit excluded). Vice versa, the open-label exposure period begins with the first documented intake of the open-label treatment (day of visit included).

If the open-label exposure period is not started, then the double-blind exposure period ends with the day of last intake of blinded treatment.

All of the following definitions regarding exposure will be calculated separately for the double-blind period, the nintedanib exposure period and over the whole trial.

Duration of exposure [weeks] will be calculated as

$$\frac{\text{Date of last administration} - \text{date of first administration during respective period} + 1[\text{days}]}{7}$$

Treatment interruptions between date of first administration and date of last administration during the respective period will not be subtracted from this duration of exposure.

Duration of exposure will be summarized as continuous variable [weeks] and in categories:

- Double-blind period:
 - ≤2 weeks (14 days)
 - >2 to ≤6 weeks (42 days)
 - >6 to ≤12 weeks (84 days)
 - >12 to ≤18 weeks (126 days)
 - >18 to ≤24 weeks (168 days)
 - >24 weeks (168 days)

- Nintedanib exposure period:
 - ≤2 weeks (14 days)
 - >2 to ≤6 weeks (42 days)
 - >6 to ≤12 weeks (84 days)
 - >12 to ≤24 weeks (168 days)
 - >24 to ≤36 weeks (252 days)
 - >36 to ≤52 weeks (364 days)
 - >52 to ≤64 weeks (448 days)
 - >64 to ≤76 weeks (532 days)
 - >76 weeks (532 days)

Further categories might be defined if needed.

Duration of exposure on dose assigned according to weight range [weeks] will be calculated per period as

$$\frac{\text{Sum of durations on-treatment with dose effectively taken according to weight range [days]}}{7}$$

Duration of exposure on reduced dose due to AE [weeks] will be calculated per period as

Sum of durations on-treatment with reduced dose effectively taken due to AE [days]

7

Calculating the duration of exposure on dose assigned according to weight range and on reduced dose due to AE, time periods with treatment interruptions as well as on dose reduced due to other reasons will be excluded.

In case the weight of the patient on reduced dose reduces in a way to match this lower dose level, the duration of exposure on reduced dose ends.

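### A missing last-dose date is imputed up to the End of Study contact, not the End of Treatment visit, so off-drug follow-up can be counted as exposure

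*SAP*

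**What the plan says.** **The rule.** SAP 6.6.3.3.1: "A missing or incomplete date of last trial drug intake will be imputed that the derived date is the latest possible date". The section sets two upper limits only: death, and the contact date taken from the End of Study page. It covers both wholly missing and partial dates. Neither this section nor any other part of the SAP names the EoT visit as a bound.

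**Follow-up after stopping.** The protocol separates stopping drug from leaving the trial.
- Flow Chart footnote (**): "Patients who discontinue trial treatment prematurely should undergo the End of Treatment (EoT) visit as soon as possible".
- Protocol 3.1: "Patients who prematurely discontinued trial medication will be asked to remain in the study and return to all regularly scheduled visits".
- Protocol 3.3.4.1, on patients who stop: "it is of utmost importance for the robustness and integrity of the trial results that the patient remains in the study".
- Protocol 6.2.2: at the EoT visit the site registers end of treatment in IRT and collects returned medication.

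**What depends on the date.**
- SAP 5.4.3: exposure runs from first to last administration, and interruptions are not subtracted. If open-label drug was never started, "then the double-blind exposure period ends with the day of last intake of blinded treatment".
- SAP 6.1: last intake plus 28 days closes the safety on-treatment window; the day after last intake closes the efficacy one.
- SAP 7.8.1 and 7.8.1.2: the same window sets treatment-emergent status and AE time at risk.

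**Limit on the primary safety endpoint.** Protocol 7.2.2 and SAP 5.1 restrict it to the double-blind period up to week 24.

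**The concern.** Taking the latest possible date works when stopping drug and leaving the study nearly coincide. Here they need not: the End of Study contact can come a year or more after the last dose, while a dated visit close to that dose already exists. For a wholly missing date, the rule can place last intake long after the drug was handed back.

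Three things then go wrong for that child. Exposure is overstated. AEs that began off drug become treatment-emergent. Off-drug person-time enters the denominators of the AE rates. In a trial whose purpose is to describe exposure and safety in about 30 children, a single case can be visible.

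**Working it through.** The plan states no figure for this rule, so there is none to reproduce. The check applies the SAP's own formulas to assumed dates. The End of Study contact is taken to be the child's last day in the trial.

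**1. Exposure, wholly missing date.** Formula (SAP 5.4.3): (last administration − first administration + 1) / 7. The child stops at the end of week 12, so true exposure is 84/7 = 12.0 weeks.

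| End of Study | Imputed last intake | Exposure under the rule |
|---|---|---|
| Week 52 | day 365 | 365/7 = 52.1 weeks |
| Week 76 | day 533 | 533/7 = 76.1 weeks |
| Week 100 | day 701 | 701/7 = 100.1 weeks |

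Capping at an EoT visit assumed 7 days after the last dose gives 91/7 = 13.0 weeks in every row.

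**2. AE time at risk, same child, no event.** Correct value: 84 + 28 = 112 days. Under the rule: 365, 533 or 701 days. The excess is (365 − 112)/365.25 = 0.69, (533 − 112)/365.25 = 1.15 or (701 − 112)/365.25 = 1.61 patient-years. For scale, Protocol 3.2 expects average nintedanib exposure of about 12 months, or roughly 30 patient-years for 30 children. One such child on nintedanib adds about 2%, 4% or 5% (0.69/30, 1.15/30, 1.61/30).

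**3. Partial date.** Assume first dose 11 January 2021 and true last dose 4 April 2021 (day 84).
- Month and year known: imputed 30 April, 110/7 = 15.7 weeks.
- Year only: imputed 31 December, 355/7 = 50.7 weeks.

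With the month known, the error is at most about a month.

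**4. Double-blind time at risk up to week 24.** One child (an assumption) stops blinded drug on day 42 and never starts open-label drug. All others contribute 168 days, for an AE that nobody had. The correct contribution is 42 + 28 = 70 days; under the rule, capped at week 24, it is 168.
- Placebo, 10 children: correct 9 × 168 + 70 = 1,582 days; rule 10 × 168 = 1,680; ratio 1.06.
- Nintedanib, 20 children: correct 19 × 168 + 70 = 3,262 days; rule 20 × 168 = 3,360; ratio 1.03.

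**5. Primary safety endpoint.** It is a count of patients with at least one AE. This child changes it only if the first AE falls after day 70 and by week 24, so the count moves by at most one.

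**6. Which periods are affected.** If open-label drug was started, SAP 5.4.3 ends blinded exposure at the first open-label intake. The error then falls on the open-label, nintedanib-exposure and whole-trial periods.

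**7. DBL 1.** SAP 7.1 expects ongoing patients at the primary cut-off. A child off drug but still attending should have no End of Study page yet, so the rule has no usable upper bound. The long imputed dates therefore arise mainly at DBL 2.

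**The case against.** **The trigger is narrow.** Protocol 3.3.4 requires discontinuation to be documented in the eCRF, last intake has a place on the End of treatment page (SAP Table 5.4.3: 1), and medication is collected at EoT. A site still seeing the child can be queried. A wholly missing date is more plausible after loss to follow-up, where the last contact date is a reasonable bound. This stands: the case is probably rare, though the documents give no rate.

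**The latest date is a cautious safety convention.** It avoids dropping AEs from the on-treatment window. This stands only in part, because it also enlarges exposure and rate denominators, and in the placebo arm it can add events to the comparator.

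**Other rules already limit the damage.** First open-label intake closes blinded exposure. SAP 6.1 treats a blinded interruption with no restart as early discontinuation. SAP 7.8.1.2 also caps time at risk at last contact, death and database lock. These help, but none supplies a bound near the true stop for a child who stays in follow-up with no stop or interruption date recorded.

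**A stronger reading is not supported.** A reader might infer that an AE at, say, week 60 would enter the primary safety endpoint. Protocol 7.2.2 and SAP 5.1 stop that endpoint at week 24. A reader might also let double-blind time at risk run to End of Study. In the placebo case of step 4 that gives 1,512 + 365 = 1,877, 1,512 + 533 = 2,045 or 1,512 + 701 = 2,213 days against 1,582, or +19%, +29% or +40%. For nintedanib it gives 3,192 + 365 = 3,557, 3,192 + 533 = 3,725 or 3,192 + 701 = 3,893 against 3,262, or +9%, +14% or +19%. Those figures rest only on SAP 7.8.1 not repeating the week-24 limit in its definition of the double-blind period. That silence means the double-blind tables could run longer for a child who never starts open-label drug, but it does not override the stated endpoint.

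**Conclusion.** The rule as written gives a wrong date in this design when the last-dose date is wholly missing and the child stayed in the trial off drug. Exposure can then be overstated by 40 to 88 weeks (52.1 − 12.0 to 100.1 − 12.0) for a stop at week 12. This carries into whole-trial and, for a child who took nintedanib, nintedanib-exposure durations, treatment-emergent status and AE time at risk, mostly at DBL 2.

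For the primary safety endpoint the consequence is small: at most one patient per affected child. Double-blind time at risk up to week 24 rises by about 6% (placebo) or 3% (nintedanib) for one affected child.

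The sizes rest on one assumed child, assumed stop and End of Study dates, the planned arm sizes, and reading the End of Study contact as the child's last day in the trial. It should not be inferred that every child who stops early is miscounted; a recorded date, or a known month and year, removes nearly all of the error. This is a correction worth making because it is cheap and the rule is wrong as written, not because the primary result is in danger.

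**What to change.** In SAP 6.6.3.3.1, impute the latest possible date on or before the earliest of death, the EoT visit date and the End of Study last contact date. Rely on the End of Study bound only where no EoT visit took place. Where there is no End of Study page yet at DBL 1, use the date of last contact as defined in SAP Section 5, or the data cut-off.

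Two clarifications belong with it. Name the End of Study field that is meant, since SAP Section 5 ties the last successful contact date on that page to patients lost to follow-up and lists the end of participation date separately. Repeat the week-24 limit in SAP 7.8.1 for the primary safety table.

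The cost is one clause plus two short clarifications and the matching program change. The EoT visit is already scheduled and registered in IRT, so no new data are needed.
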